##### 14.4.2. Primary Analysis of Primary Endpoints

The primary analyses will estimate the proportion of participants who experience a systemic allergic reaction (CoFAR Grade 2 and above regardless of tryptase, or CoFAR Grade 1 with elevated tryptase [ $1.2 \times$  baseline plus 2 ng/ml]) within the 90-minute post-vaccination observation period to either dose of the Pfizer-BioNTech COVID-19 Vaccine and independently the Moderna COVID-19 Vaccine for both the HA/MCD and comparison populations. These four proportions will be accompanied by their 95% exact confidence intervals.

If systemic allergic reactions are observed, we will compare the proportions of participants experiencing a systemic allergic reaction to the Pfizer-BioNTech COVID-19 Vaccine and independently to the Moderna COVID-

19 Vaccine between the HA/MCD and comparison populations. The point estimate of the differences in proportions between populations within vaccines will be reported, together with their corresponding 95% exact unconditional confidence intervals. Exact p-values will be calculated using an unconditional test, as some cell counts are likely to have an expected value less than 5. No multiplicity adjustment will be applied for these two primary endpoints. Details of the implementation of the exact unconditional confidence intervals and p-value calculations will be included in the statistical analysis plan.

#### 14.4.3. Analyses of Secondary and Other Endpoints

Similarly, the secondary analyses will estimate the proportion of participants with severe (Grade 3 or higher per [CoFAR Grading Scale for Systemic Adverse Reactions Version 3.0](#)) systemic allergic reactions within 90 minutes, Grade 2 or higher (per [CoFAR Grading Scale for Systemic Adverse Reactions Version 3.0](#)) within 48 hours, and anaphylactic reactions (Levels 1-3) per [Brighton Collaboration Criteria](#) within 90 minutes to either dose of the Pfizer-BioNTech COVID-19 Vaccine and independently to the Moderna COVID-19 Vaccine between the HA/MCD and comparison populations. Again, these estimates will be presented with their 95% exact confidence intervals. Due to the likelihood of these events to be extremely rare, no inferential analyses are planned.

An estimate of the proportion of participants with systemic allergic reactions to the first dose of the Pfizer-BioNTech COVID-19 Vaccine and independently the Moderna COVID-19 Vaccine in the HA/MCD population will be conducted. These estimates will be presented together with their 95% exact confidence intervals. Likewise, the estimate of the proportion and 95% exact confidence interval will be reported for the second dose conditional on no systemic allergic reaction to the first dose to each vaccine.

Another secondary analysis will be conducted to estimate the placebo-adjusted proportion of participants experiencing systemic allergic reactions to the first dose of either the Pfizer-BioNTech COVID-19 Vaccine and independently the Moderna COVID-19 Vaccine in the HA/MCD population. The placebo-adjusted proportions will be estimated as the differences in proportions between the first active vaccine dose versus the corresponding placebo vaccine arm. These estimates will be reported together with their corresponding 95% exact unconditional confidence intervals. Exact p-values will be calculated using an unconditional test. Details for implementation of the secondary analyses will be included in the statistical analysis plan.

Additionally, we will estimate the proportions of participants with systemic allergic reactions to the second vaccine dose (no placebo arm), first vaccine dose within the placebo arm, and their difference for the Pfizer-BioNTech COVID-19 Vaccine and independently the Moderna COVID-19 Vaccine in the HA/MCD population. These estimates will be presented together with their 95% exact confidence intervals.

Finally, we will compare the proportion of HA/MCD participants who experience a systemic allergic reaction (CoFAR Grade 2 and above regardless of tryptase, or CoFAR Grade 1 with elevated tryptase [ $1.2 \times \text{baseline} + 2 \text{ ng/ml}$ ]) within the 90-minute post-vaccination observation period to either dose of the Pfizer-BioNTech COVID-19 Vaccine (and independently the Moderna COVID-19 Vaccine, if child data are obtained) for both the adult and children populations. For this analysis, children who qualified on the basis of poorly controlled asthma will be excluded. These proportions will be accompanied by their 95% exact confidence intervals. The point estimate of the differences in proportions between the adult and child populations within vaccines will be reported, together with their corresponding 95% exact unconditional confidence intervals. This same analysis will be performed comparing the proportion of HA/MCD participants who experience a severe (Grade 3 or higher per [CoFAR Grading Scale for Systemic Adverse Reactions Version 3.0](#)) systemic allergic reactions within 90 minutes,

Grade 2 or higher (per [CoFAR Grading Scale for Systemic Adverse Reactions Version 3.0](#)) within 48 hours, and anaphylactic reactions (Levels 1-3) per [Brighton Collaboration Criteria](#) within 90 minutes to either dose of the Pfizer-BioNTech COVID-19 Vaccine (and independently the Moderna COVID-19 Vaccine, if child data are obtained) between the adult and child populations.

#### **14.4.4. Analyses of Exploratory Endpoints**

An estimate of the proportion of participants with systemic allergic reactions to either dose of the Pfizer-BioNTech COVID-19 Vaccine and independently the Moderna COVID-19 Vaccine in the HA/MCD population by baseline covariates will be conducted. For example, demographic, clinical and other measures at baseline will be examined as covariates in order to explore possible heterogeneity in the assessment of risk of systemic allergic reactions.

If the proportions of participants with systemic allergic reactions for either dose of the Pfizer-BioNTech COVID-19 Vaccine and the Moderna COVID-19 Vaccine are similar in the HA/MCD population, a pooled analysis will be conducted. This combined vaccine analysis will have a significant increase in power (>95%) and will provide a more precise estimate of the proportion difference and exact unconditional 95% confidence interval between the comparison and HA/MCD populations. As described earlier, the p-value will be calculated using an unconditional exact test.

Likewise, if the proportions of participants with systemic allergic reactions for adults and children are similar in the HA/MCD population, a pooled analysis will be conducted.

Additionally, an exploratory analysis evaluating risk factors associated with systemic allergic reactions to either dose of the Pfizer-BioNTech COVID-19 Vaccine or the Moderna COVID-19 Vaccine will be conducted if sufficient allergic reactions are observed. The details of such analysis will be described in the statistical analysis plan.

Statistical analysis is not specified here for exploratory objectives (e.g. transcriptomics), which will only be undertaken if systemic allergic reactions occur in a substantial number of participants.

#### **14.4.5. Descriptive Analyses**

Descriptive analyses will be reported separately for each vaccine and population. Continuous baseline measures will be reported using: (1) means (or geometric means) with 95% confidence intervals or (2) median with first and third quartiles, as appropriate. Categorical baseline and demographic characteristics and study disposition will be reported as frequencies and proportions. These descriptive analyses may be further stratified by gender, HA/MCD inclusion criteria, and other demographics/clinical baseline characteristics.

### **14.5. Interim Analyses**

#### **14.5.1. Interim Analysis of Primary Endpoint**

After fifty percent of participants have completed their vaccination schedule (approximately 1700 participants), a test of the primary analysis will be conducted using a two-sided alpha level of 0.001, without adjustment of the final analysis (i.e. using a Haybittle–Peto boundary). Interim analysis results will be reviewed by the DSMB. Refer to [Section 13.8.2.1 Planned DSMB Reviews](#).

#### **14.5.2. Interim Analysis of Safety Data**

The DSMB will receive periodic safety reports on enrolled participants. However, no formal interim analysis of safety data will be conducted.

#### 14.5.3. Futility Analysis

No formal futility analysis will be performed for this study.

#### 14.6. Statistical Hypotheses

All primary and secondary objectives will be based on two-sided superiority tests. For instance, the null and alternative hypotheses for the primary objectives are:

- $H_0$ : The proportion of participants with systemic allergic reactions in the comparison population is equal to the proportion of participants with systemic allergic reactions in the HA/MCD population
- $H_A$ : The proportion of participants with systemic allergic reactions in the comparison population is different from the proportion of participants with systemic allergic reactions in the HA/MCD population

#### 14.7. Sample Size Considerations

The within vaccine sample size of 1700 participants, 1020 in the HA/MCD population and 680 in the comparison population was determined to detect a minimum proportion difference between the two populations of approximately 0.01 with at least 80% power, assuming a two-sided unconditional exact test. The proportion is assumed to be 0.0001 (1/10,000) in the comparison group and 0.01 (1/100) in the HA/MCD group (see [Table 14.7](#)). Power was calculated using an unconditional exact test, with the significance level of the test targeted at 0.05.

**Table 14.7. Expected Rates, Number of Systemic Allergic Reactions, and Sample Size**

Rate (Number) Sample Size	Pfizer-BioNTech COVID-19 Vaccine	Moderna COVID-19 Vaccine	Total (Sample)
Comparison (40%)	0.0001 (0) 680	0.0001 (0) 680	1360
HA/MCD (60%)	0.01 (10) 1020	0.01 (10) 1020	2040
Total	0.006 (10) 1700	0.006 (10) 1700	0.006 (20) 3400

Under the scenario described in [Table 14.7](#), the proportion difference within a vaccine between the two populations is estimated at 0.01 with an unconditional exact 95% confidence interval (0.003, 0.018) and unconditional exact test p-value < 0.05. This illustration shows the expected precision of the estimated proportion difference under the assumed scenario.

This sample size also allows the following precision for estimation of risk in the HA/MCD group within each vaccine sample. If no reactions are observed out of 1020, the corresponding exact 95% confidence interval is (0, 0.0036), which rules out a risk as high as 1/275. If instead, the observed proportion is 10/1020 (i.e., about 0.01), then the 95% confidence interval is (0.005, 0.018).

For children, the within vaccine sample size of 300 participants was chosen. Under this scenario, we expect 180 in the HA/MCD population and 120 in the comparison population. This will detect a minimum proportion difference between

the two populations of approximately 0.05 with approximately 80% power, assuming a two-sided unconditional exact test. The proportion is assumed to be 0.0001 (1/10,000) in the comparison group and 0.05 (1/20) in the HA/MCD group.

Furthermore, a sample size goal of 300 children into the Pfizer-BioNTech COVID-19 vaccine allows for the following precision for the estimation of risk in the HA/MCD group. If no reactions are observed out of the 180 HA/MCD participants, the corresponding exact 95% confidence interval is (0, 0.020), which rules out a risk as high as 1/50. If instead the observed proportion is 2/180 (i.e., about 0.01), then the 95% confidence interval is (0.001, 0.039).

The sample size calculations do not account for dropouts since we expect that number to be extremely low. Although vaccine is widely available, there are difficulties getting into the registration systems and few individuals who receive an initial dose do not return for the second dose.

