### **14. Statistical Considerations and Analytical Plan**

#### **14.1. Overview**

The primary research question of this study is to assess the proportion of participants who experience a systemic allergic reaction to either dose of the Pfizer-BioNTech COVID-19 Vaccine, and, independently, of Moderna COVID-19 Vaccine in HA/MCD and comparison populations. This objective will be addressed using a multi-center, randomized, initially-blinded (to the first injection), phase 2 trial in these two populations.

For adults, if no systemic allergic reactions are observed, the within vaccine sample size will be sufficient to rule out a rate as high as 1/275 in the HA/MCD population. If systemic allergic reactions are observed, the within vaccine sample size of 1700 participants was determined to detect a minimum proportion difference between these two populations of ~0.01 with at least 80% power. This translates to a true proportion of 1/100 vs. 1/10,000 in the HA/MCD and comparison populations, respectively.

For children, if no systemic allergic reactions are observed, the within vaccine sample size will be sufficient to rule out a rate as high as 1/50 in the HA/MCD population. If systemic allergic reactions are observed, the within vaccine sample size of 300 participants will detect a minimum proportion difference between the HA/MCD and comparison populations of ~0.05 with approximately 80% power. This translates to a true proportion of 1/20 vs. 1/10,000 in the HA/MCD and comparison populations, respectively.

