7.2.1. Computation of the Primary Endpoints

The primary analyses will be conducted for participants enrolled under versions 1.0 through 4.0. For each population we will estimate the proportion of participants who experience a systemic allergic reaction (CoFAR Grade 2 and above regardless of tryptase, or CoFAR Grade 1 with elevated tryptase [1.2 x baseline plus 2 ng/ml]) within the 90-minute post-vaccination observation period to either dose of the Pfizer-BioNTech COVID-19 Vaccine and independently the Moderna COVID-19 Vaccine for both the HA/MCD and Comparison populations. These four proportions will be accompanied by their 95% exact (Clopper-Pearson) confidence intervals.

A systemic allergic reaction, categorized as yes or no, is defined as a participant having a reaction to either active dose 1 or active dose 2 (categorized as yes) or to neither active dose (categorized as no). Grade 1 systemic allergic reactions will only be categorized as yes if the tryptase is elevated as determined by the VCU lab. If the tryptase cannot be evaluated for a Grade 1 event (i.e. if missing a pre-treatment and/or post-treatment value), the study management team will determine the subjects categorization based on all available data for the subject.

Participants who do not have a systemic allergic reaction to the 1st active dose and missing data for their 2nd active dose will be removed from this analysis (complete case analysis).

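### By the plan's own exact method, 0 of 180 HA/MCD children excludes about 1/49, not 1/50, and the upper limit for 2/180 should print as 0.040

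*Protocol*

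**What the plan says.** Protocol section 14.7 plans 300 children per vaccine, of whom "we expect 180 in the HA/MCD population and 120 in the comparison population". It gives two illustrations of precision for the HA/MCD children. With no reactions, "the corresponding exact 95% confidence interval is (0, 0.020), which rules out a risk as high as 1/50". With two, "If instead the observed proportion is 2/180 (i.e., about 0.01), then the 95% confidence interval is (0.001, 0.039"). Section 14.1 carries the 1/50 statement into the overview: "the within vaccine sample size will be sufficient to rule out a rate as high as 1/50 in the HA/MCD population".

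The interval type is fixed elsewhere. Protocol section 14.4.2 says "These four proportions will be accompanied by their 95% exact confidence intervals", and SAP section 7.2.1 names the method: "These four proportions will be accompanied by their 95% exact (Clopper-Pearson) confidence intervals".

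For adults, section 14.7 prints (0, 0.0036) for 0/1020, from which it rules out 1/275, and (0.005, 0.018) for 10/1020. For the difference between 10/1020 and 0/680 it prints an "unconditional exact 95% confidence interval (0.003, 0.018").

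**The concern.** A statement that a rate is ruled out is a yes/no claim: the rate is either outside the interval or it is not. Three decimals cannot settle the matter here, because the printed limit (0.020) and the rate said to be excluded (1/50 = 0.0200) are the same number at that precision. The unrounded limit has to be examined, and it falls on the wrong side.

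The upper limit for 2/180 also looks too low in its last digit.

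What is at stake is modest. Protocol section 1.1 presents the HA/MCD risk estimate and its confidence interval as a key finding, meant to reassure allergic people if the risk is low. A bound quoted in the plan should therefore be one that the planned number can deliver. Section 14.7 makes no allowance for dropout, so there is no slack in the 180.

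**Working it through.** **Inputs.** HA/MCD children: 0.60 × 300 = 180 (Protocol 14.7). Confidence level: two-sided 95%, 0.025 in each tail, Clopper-Pearson (SAP 7.2.1). Scenarios: 0/180 and 2/180 (Protocol 14.7).

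**Step 1. Confirm the method on the adult figures.** With no events the Clopper-Pearson upper limit is 1 − 0.025^(1/n). With events, the limits are beta quantiles.

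| Data | Computed | Printed |
|---|---|---|
| 0/1020 | (0, 0.00361), upper limit 1/277 | (0, 0.0036), 1/275 ruled out |
| 10/1020 | (0.0047, 0.01796) | (0.005, 0.018) |

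Both agree. The adult 1/275 is rounded to the safe side, since the limit itself is 1/277.

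**Step 2. 0/180.**
- Upper limit = 1 − 0.025^(1/180) = 0.020285 = 1/49.3. To three decimals this is 0.020, as printed.
- Direct check at 1/50: P(0 events) = 0.98^180 = 0.0263. This exceeds 0.025, so 1/50 is not excluded.
- Direct check at 1/49: P(0 events) = (48/49)^180 = 0.0244. This is below 0.025, so 1/49 is excluded.
- Number needed to exclude 1/50: ln(0.025)/ln(0.98) = 182.6, hence 183. At n = 183 the limit is 0.01996; at n = 182 it is 0.02006. At a 60% share, 183 corresponds to 183/0.60 = 305 children in all.
- A few missing children widen the gap slightly: at n = 176 the limit is 0.0207.

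**Step 3. 2/180.**
- Clopper-Pearson gives (0.00135, 0.03956), which prints as (0.001, 0.040).
- Direct check: P(X ≤ 2) at a rate of 0.039 is 0.0271, above 0.025, so 0.039 is still inside the interval. At 0.0396 it is 0.0249.
- The printed 0.039 looks like truncation of 0.0396. The adult limits in the same section are rounded (0.01796 to 0.018, 0.0047 to 0.005).

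**Step 4. Could another method explain the printed set?**
- A one-sided 95% limit or a mid-p limit gives 0.0165 for 0/180, which would exclude 1/50. Each gives 0.0029 for 0/1020, not the printed 0.0036.
- Blaker's interval gives 0.0197 for 0/180, but (0.0020, 0.0393) for 2/180 and 0.0035 for 0/1020. These do not match the printed 0.001 and 0.0036.
- Wilson and Sterne limits for 0/180 are both 0.0209 and do not exclude 1/50.

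No variant tried reproduces the whole printed set.

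**Step 5. The adult difference, 10/1020 against 0/680.** SAP 7.2.2 inverts two one-sided exact tests based on the score statistic. The exact p-value is the maximum over the full range of the nuisance rate. For the lower limit:

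| Difference tested | One-sided p, full range | Maximum with comparison rate limited to 0–0.03 |
|---|---|---|
| 0.0030 | 0.0241 | 0.0153 |
| 0.0031 | 0.0263 | 0.0162 |
| 0.0038 | 0.0488 | 0.0249 |

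The full-range maximum occurs at a comparison rate near 0.995. The p-value passes 0.025 between 0.0030 and 0.0031, so the interval is about (0.0030, 0.0181) and prints as (0.003, 0.018), as in the Protocol.

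**The case against.** The strongest reply is that nothing of substance is wrong. The printed (0, 0.020) is correct to its stated precision; the limit misses 1/50 by only 0.0003. The 180 is an expectation drawn from an enrolment goal, and three children either way is ordinary variation in a 60/40 split. The 2/180 case is illustrative, and its error is one unit in the last printed digit. All of that stands, and it is why this is a low-severity point. It does not make the 1/50 statement true at the number the plan gives.

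Two stronger readings are tempting, and the documents support neither.

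First, a reader might infer that the sponsor will end up reporting 1/50 as ruled out when it is not. Under Protocol 14.4.2 and SAP 7.2.1, reported proportions carry exact intervals computed from the observed data, so the planning sentence would not be carried forward. SAP 7.2.1 also limits the primary analysis to protocol versions 1.0–4.0, and SAP 7.2.2 allows descriptive reporting where a population is too small. Nor is the bound the child cohort's only purpose: Protocol 4.1 gives the question of age as a risk factor, and 14.7 also states a power target for a difference of about 0.05.

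Second, a reader might infer that the adult difference interval is wrong too and should start at 0.004. That follows only if the nuisance rate is searched near zero, where the p-value at 0.0038 is 0.0249. The exact unconditional method takes the whole range. A simple check: with the HA/MCD rate at 1 and the comparison rate at 0.9962, tables with six or more comparison non-responders are at least as extreme as the observed one, and P(Bin(680, 0.0038) ≥ 6) = 0.0475. So 0.0038 is well inside the interval, and the printed 0.003 is right.

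**Conclusion.** The point holds for the two child figures only. By the plan's own Clopper-Pearson method, 0/180 has an upper limit of 0.0203 (1/49.3), so the 1/50 claim in sections 14.1 and 14.7 just fails, and the upper limit for 2/180 rounds to 0.040 rather than 0.039. The discrepancies are about 1.4% of each limit, or three children (183 against 180).

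This rests on a two-sided 95% interval with 0.025 per tail and exactly 180 evaluable HA/MCD children. Fewer evaluable children would move the bound a little further from 1/50; 183 or more would make the 1/50 statement true.

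Severity is low. These are planning figures at rounding level, with no effect on the tests, the power or any adult figure, including the difference interval (0.003, 0.018).

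**What to change.** - **Sections 14.1 and 14.7:** restate the child claim as: 0/180 gives an exact 95% interval of (0, 0.0203), which rules out a risk as high as about 1/49.
- **Section 14.7:** print (0.001, 0.040) for 2/180.
- **Leave unchanged** the adult intervals and the (0.003, 0.018) interval for the difference.

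If the sponsor prefers to keep 1/50, the alternative is to plan for at least 183 evaluable HA/MCD children, about 305 children in all at a 60% share. The wording change is simpler. It costs a text correction in two places, makes one bound very slightly less favourable, and needs no change to design or analysis.

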## **15. Identification and Access to Source Data**

### **15.1. Source Data**

Source documents and source data are considered to be the original documentation where participant information, visit consultations, examinations, and other information are recorded. Documentation of source data is necessary for the reconstruction, evaluation and validation of clinical findings, observations and other activities during a clinical trial.

The investigator should retain all documentation relating to the study (including but not limited to ICFs, source documentation, study vaccine records, eCRFs, and essential documents) for a period of at least 2 years after the last marketing application approval or, if no application will be filed or if the application is not approved, 2 years following the discontinuation of the investigation.

If this requirement differs from any local regulations, the local regulations will take precedence unless the local retention policy is less than 2 years.

At study closure, the investigator must inform DAIT/NIAID, or the SACC as designee, of the long-term storage location of the study's records and must inform DAIT/NIAID if that location changes subsequently.

No study records should be destroyed without prior authorization from DAIT/NIAID.

